6.1 Is there a chance of unexpected discoveries?

Yes

No

7 Exchange, sharing or transfer of data and/or human material and/or images outside Erasmus MC

The data will be collected and stored within the Erasmus MC in the Castor program. Only anonymous data will be collected and shared with collaborating colleagues from the EAU Pediatric Urology guidelines panel from their respective institutions outside the Erasmus MC. The institutions are:

- University of Leuven, Leuven, Belgium

- Medical University of Innsbruck, Innsbruck, Austria
- Hacettepe University, Ankara, Turkey
- University Medical Center Groningen, Rijks University Groningen, Groningen, The Netherlands
- Istanbul Biruni University, Istanbul, Turkey
- East of England Deanery, Urology, Cambridge, United Kingdom
- University of Medical Center Mannheim, Heidelberg University, Mannheim, Germany
- Aarhus University, Aarhus, Denmark
- Fondazione IRCCS Ca' Granda, Ospedale Maggiore Policlinico, Milan, Italy
- Pediatric Hospital Bambin-Gesù, Rome, Italy
- Radboud University Medical Center, Nijmegen, The Netherlands
- University of Zurich, Zurich, Switzerland
- Beacon Hospital, Dublin, Ireland

8 Statistical analysis

8.1 Main study parameter/endpoint:

The primary parameter is to evaluate quality of life in children with spina bifida using the QUALAS questionnaire. We will evaluate the differences in quality of life between European countries. Also, we will evaluate which demographic parameters are of influence on quality of life.
Descriptive statistics will be used.

8.2 Secondary study parameters/endpoints:

Secondary parameters will include sexual function using the outcomes of the IIEF-5/FSFI-6 questionnaires, also in relation to differences between European countries. Other parameters include organization of care, treatment received, treatment options available, which will all be extracted from the primary survey. Again descriptive statistics will be used.

9. Recruitment and consent

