12. Publication	11
13. References	11
14. Attachments	12

LIST OF ABBREVIATIONS AND RELEVANT DEFINITIONS*

CTA	Clinical Trial Agreement
De novo biobank	The information of a new data, human material or imaging collection
DMP	Data Management Plan
DPIA	Data Protection Impact Assessment
DTA	Data Transfer Agreement
EAU	European Association for Urology
Exception consent	Form Care for data Template , in Dutch: Formulier uitzondering toestemming
FSFI-6	Female Sexual Function Index – 6
GCP	Good Clinical Practice
GDPR	General Data Protection Regulation in Dutch: Algemene Verordening Gegevensbescherming
IC	Informed Consent
IFSBH	International Federation for Spina Bifida and Hydrocephalus
IFU	Instruction For Use
IIEF-5	International Index of Erectile Function – 5
MTA	Material Transfer Agreement
NWTC	Non-WMO Review Committee; in Dutch: Niet WMO Toetsingscommissie
QUALAS	QUALity of Life Assessment in patients with Spina bifida
UAVG	Dutch Act on Implementation of the General Data Protection Regulation; in Dutch: Uitvoeringswet Algemene Verordening Gegevensbescherming
WMO	Medical Research Involving Human Subjects Act, in Dutch: Wet Medisch-wetenschappelijk Onderzoek met Mensen

**Please delete abbreviations/definitions that are not applicable and add any new ones that are used in the research protocol*

PROTOCOL SUMMARY

Children with spina bifida require care from various medical and paramedical specialists throughout their life. The availability and organization of the care needed differs between the European countries. The EAU and IFSBH are both organizations with the aim to improve patient care and clinical outcomes for children with spina bifida.

We have set up a collaboration to evaluate the differences in organization of care and clinical treatment received and how this affects outcomes with regard to quality of life and sexuality.

A digital survey has been constructed which will be distributed among children and adolescents with spina bifida and their caregivers. The IFSBH and national patient organizations will send out invitations to their members. Children and adolescents from 8 – 18 years of age with spina bifida are eligible for inclusion.

The survey includes a primary survey developed in collaboration between panelmembers of the EAU pediatric urology guidelines and patient representatives. The second part includes validated questionnaires to evaluate Quality of life with the QUALAS and sexual function with the IIEF-5/FSFI-6 for boys/girls respectively.

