Primary outcome will be the quality of life in children and adolescents with spina bifida. We will evaluate if their demographic differences influence the quality of life and if differences are seen between the different European countries. Secondary outcomes include differences in sexual function, organization of care, treatment received, treatment options available, with also a focus on differences between the different European countries.

The results of this survey will be evaluated and interpreted within a sounding board group consisting of children/adolescents/adults with spina bifida, patient representatives from IFSBH and panel members of the EAU Pediatric Urology guidelines panel. Finally, the interpreted results will be used to update the EAU Pediatric Urology guidelines to make these more patient centered.

There are no known risks of participating in the study given the fact that participation includes only completion of questionnaires and data about standard of care. Furthermore, the study is completely voluntary and the results will be completely anonymous.

1. Introduction and rationale

Children with spina bifida require care from various medical and paramedical specialists throughout their life. The availability and organization of the care needed differs between the European countries. It can be expected that this variety results in differences in outcome of care.

Children with spina bifida have stated that for future research they feel it is important that quality of life and sexuality are investigated. [1]

The EAU Pediatric Urology guidelines panel wants to ensure that patients with spina bifida receive the best possible care based on the best available clinical evidence. [2] Additionally, we want to improve the clinical guidelines by including patients perspectives. The IFSBH represents patients with spina bifida and values the promotion and protection of the human rights of patients with spina bifida thereby improving quality of life.

Together with the IFSBH we have set up a collaboration to investigate how we can make the guidelines more patient centered and thereby improve quality of care and quality of life.

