For this aim we have developed a survey to evaluate the current organization of care, demographic features and received treatment. The outcome of this survey will show the exact differences in care between European countries. We have included two validated questionnaires to measure the effect this has on quality of life and sexuality. The information gathered will be used to adapt the clinical EAU Pediatric Urology guidelines.

2. Objective(s)

The main objective is to improve the quality of life of patients with spina bifida by updating the guidelines according to the differences found in care and how this impacts patients outcomes. We will evaluate the difference in organization of care between different European countries based on the outcomes of the primary survey. The baseline quality of life and sexuality reported will be evaluated with the QUALAS and the IIEF-5/FSFI-6 questionnaires [3-6]. We will then explore the relationship between how care is organized and how this affects quality of life and sexuality. The results of this study will be used to update the EAU Pediatric Urology clinical guidelines. Also, it will highlight the direction for future research to improve patients care and thereby quality of life and/or sexuality, which patients with spina bifida have stated they themselves find important.

3. Study type

3.1 Study type:

- Retrospective
- Prospective
- Combination Retrospective/Prospective

3.2 Check all the applicable boxes:

- Medical records (re-use of data from healthcare, including AI)
- Case report
- Re-use data from research
- Evaluations of quality of healthcare (retrospective)

QoL in patients with spina bifida

- Research with additional use of residual material from regular healthcare
- Research with re-use of human materials from research or existing biobank
- Research with human materials without biobank
- De novo biobank (human material obtained without burdensome or invasive procedures)
- Post marketing survey research with medical devices
- Phase IV research
- Healthcare evaluation research (prospective)
- Medical devices
- In Vitro Diagnostic Tests
- Other research, *describe*

4. Study population

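### Section 8 commits only to descriptive statistics, although the plan asks what influences quality of life and how organisation of care relates to it

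*Combined protocol and SAP*

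**What the plan says.** Section 8.1 makes QUALAS quality of life the primary parameter and attaches two questions to it. One is how it differs between European countries. The other is: "Also, we will evaluate which demographic parameters are of influence on quality of life". The method follows in one sentence: "Descriptive statistics will be used". Section 8.2 takes sexual function (IIEF-5 or FSFI-6) as a secondary parameter, also by country. It lists organisation of care, treatment received and treatment options as further items from the primary survey, and closes with "Again descriptive statistics will be used".

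Section 2 adds a third question: "We will then explore the relationship between how care is organized and how this affects quality of life and sexuality". Section 1 says of the outcome instruments: "We have included two validated questionnaires to measure the effect this has on quality of life and sexuality". The protocol summary uses similar language: "We will evaluate if their demographic differences influence the quality of life and if differences are seen between the different European countries". It also describes the collaboration as looking at "organization of care and clinical treatment received and how this affects outcomes".

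Section 4.4 calls the study descriptive, requires no minimum sample size and aims for 500 patients. Section 5.1 says that QUALAS has one version for ages 8-12 and another for 13-18. The intended use is given in the summary: "the interpreted results will be used to update the EAU Pediatric Urology guidelines".

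**The concern.** The method and the questions do not match. Whether a demographic characteristic influences quality of life, and whether organisation of care affects it, are questions about association at the least, and the wording suggests cause. A mean per country or per demographic group cannot answer them alone, because countries may differ in the age, sex or other characteristics of those who respond. The care question is worse placed: Section 8 lists the care variables and the outcomes but never relates one to the other.

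The stake is the guideline update. If differences reach the sounding board without a stated uncertainty, its members cannot judge which ones could be sampling error. If intervals, covariates and country groupings are chosen only after the data have been seen, those choices carry less weight than ones fixed beforehand.

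**Working it through.** **1. Questions against methods.**
- Country differences in quality of life (8.1): descriptive statistics. Summaries by country can describe these, but no interval, adjustment or minimum country size is stated.
- Demographic influence on quality of life (8.1, summary): descriptive statistics. No covariate list or model is stated.
- Organisation of care in relation to quality of life and sexuality (Section 2, Section 1, summary): no analysis in Section 8.
- Sexual function by country (8.2): descriptive statistics, with no interval stated.

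No confidence interval, regression, adjustment set, precision target or rule for handling the two QUALAS versions appears anywhere in the document.

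**2. Why simple summaries do not separate the factors.** Suppose two groups of a demographic factor differ in mean score by δ, and the share of the first group differs by p between two countries. The unadjusted country difference then contains p × δ that has nothing to do with country. The same holds in reverse for a demographic contrast when countries differ.

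**3. Illustrative precision.** The 500 is an aim with no derivation, so there is no plan figure to reproduce. Inputs: N = 500 (Section 4.4). Assumed: scores in SD units (SD = 1) and k countries of equal size with k = 5, 10 or 20. The documents give neither the SD nor the number of countries.

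95% half-width for the overall mean: 1.96/√500 = 0.088 SD.

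95% half-width for a two-country difference: 1.96 × √(2k/N).
- k = 5 (100 per country): 1.96 × √(10/500) = 0.28 SD
- k = 10 (50 per country): 1.96 × √(20/500) = 0.39 SD
- k = 20 (25 per country): 1.96 × √(40/500) = 0.55 SD

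Unequal countries, for example 20 against 150 respondents: 1.96 × √(1/20 + 1/150) = 0.47 SD.

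Demographic factor split 50:50: 1.96 × √(1/250 + 1/250) = 0.18 SD.

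**4. If the two QUALAS versions are analysed separately.** With ages spread evenly over 8 to 18 (assumed), 500 × 5/11 = 227 respondents get the younger version and 500 × 6/11 = 273 the older. The same formulas give:
- ages 8-12: 0.41, 0.58 and 0.82 SD for k = 5, 10 and 20; 50:50 factor 1.96 × 2/√227 = 0.26 SD
- ages 13-18: 0.38, 0.53 and 0.75 SD for k = 5, 10 and 20; 50:50 factor 1.96 × 2/√273 = 0.24 SD

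So the overall mean would be estimated tightly and a balanced demographic contrast fairly well, while a two-country difference could be quite uncertain.

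**The case against.** The strongest reply is that the study calls itself descriptive (Section 4.4) and demographic (Section 5.2). Such a study needs no power calculation, and country summaries do describe country differences. That stands, and nothing here asks for a power calculation or says that 500 is wrong.

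It is also fair that descriptive statistics can include confidence intervals and tables stratified by age or sex. A reader might infer that the plan excludes these. It does not; it simply does not commit to them.

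A reader might infer that the two QUALAS versions must be kept apart, so that every comparison uses only part of the 500. The documents say that there are two versions, not that their scores cannot be combined. The separate-version figures are therefore conditional.

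A reader might also infer that countries will be ranked, or that chance differences will drive recommendations. No section says so. The results first go to a sounding board, the aim is a more patient-centred guideline, and Section 2 words the care question as exploration. Every analysis proposed here could still be run later on the stored data, so no information is lost.

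What the reply does not remove is that the wording of the aims goes beyond a description by country, that no adjustment is planned, and that the care question has no analysis at all.

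**Conclusion.** The point holds and should be fixed before the data are examined. From the text alone, Section 8 names only descriptive statistics for questions about influence and association, states no precision, and leaves the care aim of Section 2 without an analysis. That conclusion needs no assumption.

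The size is illustrative. A two-country difference at 500 has a 95% half-width of 0.28 to 0.55 SD for 5 to 20 equal-sized countries, wider by QUALAS version, against 0.18 SD for a 50:50 demographic contrast. These figures rest on an assumed number of countries, equal sizes and SD units. They show what a reader would need to be told; they do not show an error in the 500.

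**What to change.** **Section 8.1.** Report QUALAS by country and by demographic group with n, mean, SD and 95% CI, by age version unless the instrument's scoring supports pooling. Add a linear regression of QUALAS on country, age, sex and a demographic list taken from the primary survey and fixed before the data are examined, with 95% CIs and one overall test for country. Only describe countries below a minimum size fixed in advance. Justify that size by the precision it gives, and state whether it applies overall or per version. For scale, two countries of 10 respondents each give 1.96 × √(2/10) = 0.88 SD, and two of 50 give 0.39 SD.

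**Care aim.** Add to Section 8 an exploratory table of QUALAS, IIEF-5 and FSFI-6 by organisation of care and treatment received, with 95% CIs. Only describe care features that do not vary within a country, since they cannot be separated from country.

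**Section 8.2.** Use the same interval reporting, separately for IIEF-5 and FSFI-6.

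**Wording.** In the summary and Sections 1, 2 and 8, replace the language of influence and effect with *associated with*. State that results are associations among self-selected respondents, that the intervals do not cover self-selection, and that associations with treatment may reflect severity.

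**Cost.** A few sentences and a little more analysis of data already to be collected, with no new patients. Differences will look less certain. Adjustment can use only what the primary survey records, and the questionnaire is an attachment not reproduced in the text, so the covariate list has to be drawn up by the sponsor. Neither intervals nor models correct for self-selection.

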4.4 Sample size calculation

Since this is a descriptive study no minimal sample size is required.

However, our aim is to include 500 patients.

4.5 (Planned) start date

Depending on the approval of the NWTC.

Start date 01.01.2023.

4.6 (Planned) end date

The digital questionnaire will be available for 3 months.

5 Methods

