5.1 A digital survey has been created on Surveymonkey: <https://www.surveymonkey.com/r/7WSB9S9>

This digital survey includes a primary survey regarding basic demographic features, medical treatment and organization of care. This survey was constructed by the EAU guidelines panel and the IFSBH patient representatives. The second part of the digital survey includes two validated questionnaires. The QUALAS is a validated questionnaire regarding quality of life in patients with spina bifida. There are two different versions for the ages 8-12 and 13-18 years. To evaluate sexuality the IIEF-5 (for boys) and the FSFI-6 (for girls) are used. These questionnaires are validated and are used in patients with spina bifida to evaluate sexual function as standard of care. Only children aged 13 years or older will be asked if they want to answer questions about sexuality and if they answer yes they will be asked for which gender they want to answer questions about their sexuality. After this they'll get the IIEF-5 or FSFI-6 questionnaire.

This digital survey is available in nine languages: English, Spanish, German, Italian, French, Danish, Greek, Turkish and Dutch.

The link to surveymonkey will be distributed by the IFSBH and local patient organizations among their members.

After the data have been collected, the general results of the survey will be evaluated and interpreted with a sounding board group. When patients participate with the digital survey they will not be involved in the sounding group. This sounding board group will consist of children/adolescents/adults with spina bifida who are representatives from the patient organization IFSBH and panel members of the EAU. This sounding board group will meet for a day. Finally, the results will be used to update the EAU Pediatric Urology guidelines.

5.2 This is a demographic study. Patients will not receive any difference in treatment.

5.3 The survey only has to be completed once and is completely voluntary. The questionnaire will take around 15 minutes to complete. It will not influence their own treatment.

5.4 There are no known risks of participating in the study given the fact that involves only the completion of questionnaires and data about standard of care. Also, all responses will be anonymous and completely voluntary. No personal identifying information will be used when reporting the data.

6 Unexpected discoveries

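### Section 8.1 looks for demographic influences on quality of life without stratifying or adjusting by country, so a feature unevenly spread over countries would pick up part of any country gap

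*Combined protocol and SAP*

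**What the plan says.** Section 8.1 gives the QUALAS primary parameter two tasks. One is the country comparison: "We will evaluate the differences in quality of life between European countries". The other is demographic: "Also, we will evaluate which demographic parameters are of influence on quality of life". One sentence on method covers both: "Descriptive statistics will be used". The protocol summary sets the same two aims side by side without linking them: "We will evaluate if their demographic differences influence the quality of life and if differences are seen between the different European countries".

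Three other places bear on the point.

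- Section 1, on the variation in care between European countries: "It can be expected that this variety results in differences in outcome of care". No size is given.
- Section 5.1, on recruitment: "The link to surveymonkey will be distributed by the IFSBH and local patient organizations among their members". Section 9.1 adds that this is done by email and newsletter. No country quotas, weights or target mix are stated.
- Section 4.4, on numbers: "Since this is a descriptive study no minimal sample size is required", followed by "However, our aim is to include 500 patients".

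Nowhere do the documents say that the demographic comparison will be made within country, standardised, or adjusted for country.

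**The concern.** Two conditions together distort a demographic contrast taken over all respondents: quality of life differs between countries, and the demographic feature is commoner among respondents in some countries than in others. The protocol expects outcomes to differ by country. It does not assert the second condition, but voluntary response through separate patient organizations does nothing to prevent it.

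Where both hold, the crude difference in QUALAS between respondents with and without the feature adds part of the country gap to the within-country association. A feature with no association in any country can then appear to matter, or a real association can be hidden or reversed. Measuring the country differences well, as the other half of 8.1 intends, does not remove this from the demographic half.

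The demographic question belongs to the primary parameter, 8.1 words it as influence, and section 5.1 says the results will be used to update the guideline.

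**Working it through.** **The plan's own figure.** The 500 in section 4.4 is an aim with no effect size, SD, error rate or number per country behind it, so there is no calculation to reproduce. What follows is an illustration.

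**Inputs.** From the documents: n = 500 (section 4.4). Assumed: all 500 enter one contrast; two country blocks of 250; within-block SD of 1; no true association within either block; a gap *g* of 0.5 or 0.3 SD between blocks; a yes/no feature with prevalence 20% and 60%, or 30% and 50%, in the lower- and higher-scoring block.

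**Spurious difference.** Expected crude difference = *g* × (share from the higher block among those with the feature − the same share among those without it).

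- 20% and 60%: shares are 0.6/0.8 = 0.750 and 0.4/1.2 = 0.333, a difference of 0.417.
- 30% and 50%: shares are 0.5/0.8 = 0.625 and 0.5/1.2 = 0.417, a difference of 0.208.
- Equal prevalence: the shares are equal and the spurious difference is zero whatever the gap.

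**Standard error.** In both cases 40% have the feature, so the groups are 200 and 300. With within-block variance only, SE = √(1/200 + 1/300) = 0.0913. The mixing of blocks inside each group adds *g*² × share × (1 − share) to that group's variance. For *g* = 0.5 at 20%/60%, the variances are 1 + 0.25 × 0.1875 = 1.047 and 1 + 0.25 × 0.2222 = 1.056, so SE = √(1.047/200 + 1.056/300) = 0.0936.

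| Gap (SD) | Prevalences | Spurious difference (SD) | SE | Difference / SE |
|---|---|---|---|---|
| 0.5 | 20%, 60% | 0.5 × 0.417 = 0.208 | 0.0936 | 2.2 |
| 0.5 | 30%, 50% | 0.5 × 0.208 = 0.104 | 0.0940 | 1.1 |
| 0.3 | 20%, 60% | 0.3 × 0.417 = 0.125 | 0.0921 | 1.4 |
| 0.3 | 30%, 50% | 0.3 × 0.208 = 0.0625 | 0.0923 | 0.7 |

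Only the first row exceeds two standard errors.

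**Effect of the two QUALAS versions.** Section 5.1 gives separate versions for ages 8–12 and 13–18. If they are analysed separately and respondents split evenly (assumed), each contrast has 250 respondents and the ratios fall by √2; the largest becomes 2.2/√2 ≈ 1.6. The expected spurious difference itself does not shrink.

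**Does adjustment remove it?** A simulation with the same two-block structure and no true association (4,000 runs), using a wider spread of 30% against 70% and a 0.5 SD gap, gave a mean crude difference of 0.200 SD, with two-sided p < 0.05 in 58.8% of runs. With a country term the mean was −0.001 SD and the rate 5.2%. The p < 0.05 threshold is only a yardstick; the plan names no test.

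**Cost in precision.** At 20%/60% the average within-block variance of the feature is ½(0.2 × 0.8) + ½(0.6 × 0.4) = 0.20. The country-adjusted SE is about 1/√(500 × 0.20) = 0.100. That is about 10% above 0.0913, or about 7% above 0.0936.

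**The case against.** A reader might infer that 8.1 commits the study to a pooled, confounded table. It does not. It prescribes no table layout, and description by country would also fit its wording. What stands against the plan is narrower: it states no stratification or adjustment, and a question about which parameters matter, asked of the study as a whole, reads most naturally as a comparison over all respondents.

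A reader might also infer that the distortion is known to be present or large. The documents do not support that. They give no size for the country gap and do not list the demographic features. Nothing in them suggests that age (restricted to 8 to 18) or sex would be spread as unevenly as 20% against 60%. Three of the four scenarios fall below two standard errors.

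It is also fair to say that crude summaries are a legitimate product of a descriptive study, that a sounding board interprets the results before guideline use, and that adjusting for country alone leaves other confounding. The first two do not remove the bias: calling a contrast descriptive does not change what it mixes, and a sounding board cannot separate country from feature in a crude table. The third stands. Country adjustment would not justify the language of influence, so the wording needs changing as well.

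**Conclusion.** The concern holds as a gap in the primary analysis that should be closed. The mechanism is certain once its two conditions are met; its size in this study is unknown. The protocol expects the first condition and leaves the second uncontrolled. Under the assumed inputs the spurious difference runs from 0.06 to 0.21 SD, or about 0.7 to 2.2 standard errors with 500 respondents in one contrast, and fewer standard errors if the QUALAS versions are analysed separately. Features evenly spread over countries are unaffected. These figures show what could happen under stated assumptions; they do not predict the results. The change is worth making because it replaces an unspecified comparison with a better one, using a variable that 8.1 already needs.

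**What to change.** In section 8.1:

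1. State that each demographic difference in QUALAS is estimated within country and the within-country differences combined, by a stratified mean difference or a linear model with a term for each country.
2. Show the crude table beside the within-country result, so that readers can see how far they differ.
3. Fix, before the data are examined, a minimum number of respondents below which countries are grouped, and say how the groups are formed.
4. Write 'associated with' in place of 'of influence on', and make the matching change in the protocol summary.

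No extra data are needed, because the country comparison already requires country. The costs are some loss of precision (about 10% on the standard error in the 20%/60% example, and more for a feature that hardly varies within countries) and possible residual country confounding inside any merged group of small countries. The second matters because recruitment sets no number per country, so several may be small.

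### Does section 8.2 need to fix how country differences in sexual function are reported, given small opt-in cells and only descriptive statistics?

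*Combined protocol and SAP*

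**What the plan says.** Section 8.2 sets the secondary parameter: "Secondary parameters will include sexual function using the outcomes of the IIEF-5/FSFI-6 questionnaires, also in relation to differences between European countries". On method it adds only this: "Again descriptive statistics will be used".

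Section 5.1 limits who contributes: "Only children aged 13 years or older will be asked if they want to answer questions about sexuality". Those who accept choose the gender for which they will answer: "After this they'll get the IIEF-5 or FSFI-6 questionnaire". The first part of the survey does not concern sexuality: "This digital survey includes a primary survey regarding basic demographic features, medical treatment and organization of care".

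Section 4.4 calls the study descriptive, sets no minimum sample size and aims for 500 patients. Section 4.1 gives the age range as 8 to 18.

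On purpose, section 1 says: "We have included two validated questionnaires to measure the effect this has on quality of life and sexuality". Section 2 says: "We will then explore the relationship between how care is organized and how this affects quality of life and sexuality". The protocol summary says: "The results of this survey will be evaluated and interpreted within a sounding board group", and the interpreted results are then to inform a guideline update.

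The protocol does not say whether country figures will carry counts or confidence intervals, whether the number accepting the sexuality questions will be reported, or how very small countries will be shown.

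**The concern.** The sample of 500 is thinned four times before a country result on sexual function exists: by age, by opt-in, by instrument and by country. What remains could be a handful of teenagers per cell. Means from such cells differ by chance alone, and a table of bare country means would invite readers to see differences in care where there may be none.

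Opt-in adds a second worry. If willingness to answer differs between countries, a country contrast may partly reflect who chose to answer, and an interval would not reveal that.

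At stake is whether the sounding board, and then the guideline panel, takes noise or selection for a real country difference. Sections 1 and 2 use the language of effect, which makes the worry more natural. The primary parameter, quality of life, is not affected.

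**Working it through.** The plan gives no precision target, SD, effect size or error rate, so there is no figure of its own to reproduce beyond the aim of 500. The check asks how small the cells could be and what follows.

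**Inputs from the protocol.** Aim of 500 (4.4); ages 8 to 18, which is 11 year-ages (4.1); sexuality questions from age 13, which is 6 of those 11 (5.1); two instruments (5.1).

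**Assumed inputs.** Even ages, a 50:50 instrument split, opt-in of 30 to 100%, and 5 to 20 countries of equal size. Ten is a convenient central number because the institutions listed in section 7 lie in 10 countries, but the protocol does not say where respondents will live.

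**Cell size.** Teenagers: 500 × 6/11 = 273. Per instrument: 273/2 = 136. With 10 countries:

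| Opt-in | Per instrument | Per country per instrument |
|---|---|---|
| 30% | 41 | 4 |
| 50% | 68 | 7 |
| 80% | 109 | 11 |
| 100% | 136 | 14 |

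The extremes are 136.4 × 0.3/20 = 2 and 136.4/5 = 27.

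**Two-country difference.** The 95% half-width in SD units is t(2n−2) × √(2/n). It is 1.73 at n = 4, 1.16 at n = 7, 0.89 at n = 11, 0.78 at n = 14 and 0.55 at n = 27.

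**Unequal countries.** Suppose two large countries hold 25% and 20% of respondents. At 50% opt-in they have 17 and 14 per instrument, and t(29) × √(1/17 + 1/14) = 0.74 SD. At 100% opt-in they have 34 and 27, giving 0.52 SD.

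**Chance gap between the highest and lowest country mean, with no true difference** (simulation, normal scores):

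| Countries | n per cell | Mean gap (SD) | Share of samples with gap above 0.5 SD |
|---|---|---|---|
| 10 | 7 | 1.16 | over 99% |
| 10 | 14 | 0.82 | about 95% |
| 5 | 14 | 0.62 | about 67% |
| 5 | 27 | 0.45 | about 35% |

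These figures describe the two extremes out of all the countries, and the protocol does not plan to rank countries. For one pair fixed in advance, 34 against 27, the standard error is √(1/34 + 1/27) = 0.258 SD. A chance difference above 0.5 SD, in either direction, then occurs about 5% of the time (0.5/0.258 = 1.94).

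**Whole-sample means.** With t(n−1)/√n, the half-widths are 0.32, 0.24, 0.19 and 0.17 SD at 30, 50, 80 and 100% opt-in. These are usable.

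**Opt-in check.** One could compare QUALAS between those who accept and those who decline. Assume that sexual function correlates 0.2 to 0.5 with willingness to answer and 0.3 to 0.5 with QUALAS. For opt-in rate p, and z the matching normal quantile, the expected QUALAS gap is the product of the two correlations × φ(z)/(p(1−p)). Over p = 0.3 to 0.8 this runs from 0.10 to 0.44 SD. The half-width of the comparison among 273 teenagers is 0.24 to 0.30 SD, so the check would detect selection somewhere between about 10% and 91% of the time. The correlations have no source in the protocol.

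**Against the wording of the plan.** Section 8.2 names descriptive statistics. That term ordinarily covers counts and can cover intervals, and nothing in the protocol excludes either. Section 4.4 declares the study descriptive, and section 2 speaks of exploring relationships. No test, threshold or confirmatory claim is attached to sexual function.

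**The case for a change.** The strongest case for a change is that a descriptive aim excuses the absence of a power calculation but not the absence of precision once countries are contrasted. The results go to a sounding board that meets for one day and then into a guideline, and sections 1 and 2 speak of effects. A few sentences would cost almost nothing: counts and 95% intervals by country and instrument, an exploratory label, and the number who accepted the sexuality questions. Imprecision between countries holds over the whole range examined; even the most favourable corner, n = 27, leaves a half-width of 0.55 SD.

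Much of this stands. Country results on sexual function are likely to be imprecise, and good reporting would show it. It does not establish a fault in the plan, because it reads silence as a decision to omit. Counts are about the most basic descriptive statistic, and nothing suggests that the analysts will withhold them.

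The opt-in comparison changes no estimate, can easily miss selection, and depends on survey routing that cannot be checked because the questionnaires were not supplied. The documents do not show that opt-in is selective.

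A requirement to show every country with its n would also bring its own difficulty. Cells of one to four teenagers sit badly with the promise in sections 9.1, 10.1 and 10.2 that data cannot be traced to an individual, and an interval cannot be computed from a single respondent. Leaving the display of small countries to the analysts' judgement, once cell sizes are known, is reasonable.

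**Conclusion.** No change to the plan is needed. The arithmetic is sound as illustration: about 7 respondents per country per instrument in the assumed central case, with a two-country half-width of about 1.16 SD. It rests on an assumed opt-in rate, age mix, instrument split, number of countries and country shares. Varying the opt-in rate and the number of countries moves the cells from 2 to 27, and the share of chance gaps above 0.5 SD from over 99% (10 countries, n = 7) to about 35% (5 countries, n = 27).

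No stated rule or figure in section 8.2 is wrong. The parameter is secondary, whole-sample results are usable at about ±0.17 to ±0.32 SD, and the study makes no confirmatory claim about countries. Counts, intervals, acceptance numbers and cautious wording about country differences are details that analysts ordinarily add when they report a descriptive survey. If the sponsor wished to write them down, one sentence covering all of section 8 would do, but the validity of the plan does not depend on it.
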